Stanley-Brown Safety Plan app (i.e., Safety Net app): The Safety Net app is an electronic version of a safety plan and it is available for download in Apple’s App Store. A preview of this app is available at: <https://apps.apple.com/us/app/stanley-brown-safety-plan/id695122998>. This app is owned by Two Penguins Studios, LLC. It was developed in partnership with the New York State Office of Mental Health. Unlike the paper version, the Safety Net app allows participants to email a copy of their safety plan to whomever they wish. It also allows patients to dial 911 or the National Suicide Prevention Lifeline from the app.

Please see Figure 2 below for study flow. The app only stores deidentified data locally on UAMS secured tablets. Thus, the safety plan will have to be shown or emailed to clinical staff in order to be entered into the electronic medical record. Please note that peers and other research staff do not have the ability to place notes in the EMR.

[figure not shown]

Figure 2. Study flow.

Study Design and Procedures

This is an effectiveness-implementation randomized controlled trial which will be conducted in the emergency department (ED) at the University of Arkansas for Medical Sciences (UAMS) in Little Rock, Arkansas. The UAMS ED is an urban emergency department which sees approximately 60,000 patients per year, including more than 1,200 suicidal patients.

This clinical trial will compare the intervention of ED patients completing an electronic safety plan with a peer or other research staff member to completing a traditional written safety plan with a peer or other research staff member. Patients triaged and flagged with the chief complaint of "SI", "suicidal ideation", "suicide attempt", or "Psychiatric BEE" on the ED trackboard when a peer or other research staff member is available will be approached to participate. Patients will be approached after evaluation by an emergency physician.

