- Prospective participants <18-years or >89-years of age;
- Presently incarcerated or in police custody;
- Non-English speaking;
- Critically-ill;
- Intoxicated with alcohol or other substances;
- ED staff objected against entering room;
- Unwilling or unable to complete the safety plan electronically;
- Unwilling or unable to use a tablet;
- Unwilling or unable to show/email this safety plan to clinical and research staff.

Title: Written safety planning vs the Safety Net app: A prospective randomized pilot trial

PI: [name], PhD

Site: University of Arkansas for Medical Sciences

If participants indicate interest in the study and meet all inclusion/exclusion criteria, informed consent will be obtained using IRB-approved consent forms & processes. If they provide consent, participants (n=30) will be randomized in a 1:1 fashion to either the traditional written safety plan group, in which they will complete a written safety plan with a peer support specialist or other research staff member, or the electronic "Safety Net" safety plan group, in which they will complete an electronic safety plan with a peer support specialist or other research staff member (please see Figure 2 above).

Participants will be randomized using the randomization function in REDCap. All participants will be allowed to complete the safety plan in the privacy of their ED treatment room. Please note that participants will be given a \$25 gift card for participating regardless of which group they are randomized into for the study.

After completing the safety planning process, participants will then be asked to answer a short questionnaire concerning their demographics (e.g., age, biological sex), any history of previous suicidal ideation, suicide attempts, or related behaviors, and satisfaction with the safety planning process.

Regardless of whether the safety plan is completed in the traditional paper format or electronically, this will be shown to the UAMS ED psychiatric registered nurse or social worker for approval and entry into the EMR. Please note that the study will not otherwise modify care in the ED. It is possible, although not likely, that psychiatry consultants could choose to revise, edit, or otherwise start anew with safety planning for a particular patient. If so, the patient will be withdrawn from the study.

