Other measures: All participants will complete a brief questionnaire regarding their demographics, history of suicidal behaviors, and satisfaction with the safety planning process. After the visit, the electronic medical record will be searched for the following data: date/time of ED triage and disposition; length of ED stay; ED chief complaint or reason for visit; patient disposition (observation/admission/discharge/transfer); psychiatric diagnoses; and frequency of ED visits 3 months before and after the intervention. Length of ED stay will be compared against two control groups (obtained using AR-CDR): a) length of stay of all ED patients during a similar time period; and b) length of stay of ED patients who presented for SI during a similar time period. No PHI will be recorded for either of these deidentified control groups. Peers and other research staff will also be asked to record the total amount of time that they spent performing the safety plan intervention.

Study retention: The study duration is limited to the ED visit (typically <6 hours for SI patients), with participation in the study limited to the interventions mentioned above. Consequently, no special measures designed to increase retention are planned.

Title: Written safety planning vs the Safety Net app: A prospective randomized pilot trial
PI: [name], PhD
Site: University of Arkansas for Medical Sciences

Recruitment of peers for this project

Peers will be recruited through existing relationships with community suicide prevention organizations (i.e., Arkansas Foundation for Suicide Prevention, Arkansas Governor's Suicide Prevention Council, Veterans Service Organizations, etc.). Eligible recruits will complete an interview with [name] where they will be informed about the responsibilities and expectations of working with this project. Training and supervision of peers and other research staff will be used to further monitor the appropriateness of the individual to assist patients in providing the intervention.

Training of peers and other nonclinical individuals

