Power calculations and sample size: As this is a pilot study, no formal sample size calculation is planned. The investigators plan a priori to enroll 30 patients. The investigators therefore ask for permission to approach a maximum of 100 patients.

Initially, the randomization scheme will be validated by comparing the groups on key variables that could be associated with outcome (e.g., age, biological sex, prior suicide

Title: Written safety planning vs the Safety Net app: A prospective randomized pilot trial

PI: [name], PhD

Site: University of Arkansas for Medical Sciences

attempts, prior completion of safety plan). Where we identify significant differences between groups, we will either adjust for these variables in analysis or conduct stratified analyses. Categorical variables will be analyzed with chi-square. Continuous variables will be analyzed by ANOVAs. Sub-analyses of potential prognosticators, including biological variables such as sex, will be descriptively presented, as the sample size will not likely permit sufficient testing of these variables.

Ethical Considerations

Written consent will be required for any study procedures. (please see “consent form.”). Please note that all study procedures will be conducted in accordance with all applicable government regulations and University of Arkansas for Medical Sciences research policies and procedures. This protocol and any amendments will be submitted and approved by the UAMS Institutional Review Board (IRB) to conduct the study.

Potential participants will be identified from the ED track board and/or patient triage note. This requires a partial waiver of HIPAA for recruitment purposes only. No PHI will be recorded or disclosed without patient consent. Please see study flow above.

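### Length of ED stay in 30 participants would be tested against much larger, overlapping hospital groups by pooled-variance ANOVA; its error rate is near 5% only if spreads are equal

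*Combined protocol and SAP*

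**What the plan says.** Under Other measures, the protocol states "Length of ED stay will be compared against two control groups (obtained using AR-CDR". The first group, (a), takes in every ED patient seen over a comparable but undated period. The second, (b), is narrower: "length of stay of ED patients who presented for SI during a similar time period". The protocol gives neither the dates nor the size of either group.

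Under Data Analysis, after the sample-size paragraph, there is one rule for this type of variable: "Continuous variables will be analyzed by ANOVAs". No unequal-variance version, transformation, rank test or descriptive-only provision is given for length of stay. The only material reserved for description is the sub-analysis of prognostic variables.

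Other relevant facts:
- Trial size: "participants (n=30) will be randomized in a 1:1 fashion".
- ED volume, from Study Design and Procedures: "approximately 60,000 patients per year, including more than 1,200 suicidal patients".
- The only length-of-stay figure, under Study retention: "typically <6 hours for SI patients".
- No mean, SD or significance level is stated for length of stay.

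**The concern.** A one-way ANOVA uses a single variance estimate for all groups. With 30 patients on one side and hundreds or thousands on the other, that estimate is essentially the controls' variance. If participants' stays vary more than the controls', the standard error is too small and false positives rise. If they vary less, it is too large and real differences are missed.

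Equal spread cannot be presumed. Participants exclude critically ill, intoxicated, in-custody, non-English-speaking and under-18 patients, whereas the all-ED group is described without any such limits.

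The second problem needs no assumption about spread. Group (b) is contained in group (a), and nothing removes participants from either extract, so the groups are not independent as ANOVA requires.

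At stake is what the report can say about how participants' stays compare with those of other ED patients. This is the only planned comparison with patients outside the trial.

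**Working it through.** The documents give no power, error rate or SD for length of stay, so there is no stated figure to reproduce.

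**Inputs from the documents.** Participants n = 30. All ED: 60,000 / 52 ≈ 1,150 per week. SI: 1,200 / 12 = 100 per month. The all-ED group therefore passes 1,000 in about a week, while the SI group needs most of a year.

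**Assumptions.** Two-sided 5% test; r = participant SD / control SD, varied from 0.67 to 2; control size m from 100 (one month of SI patients) to 60,000 (one year of all ED patients).

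**Error rate of the pooled test.** For two groups, ANOVA is the pooled t-test. With control SD set to 1:
- Pooled variance s² = [29r² + (m − 1)] / (m + 28)
- SE used = √[s²(1/30 + 1/m)]
- True SE = √(r²/30 + 1/m)
- Error rate = 2[1 − Φ(t × SE used / true SE)], where t is the 97.5% point on m + 28 df

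Example, m = 1,200 and r = 1.5: s² = (65.25 + 1,199) / 1,228 = 1.030; SE used = 0.188; true SE = 0.275; t = 1.962. The argument is 1.336 and the error rate 18.1%.

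| r | m = 100 | m = 300 | m = 1,200 | m = 60,000 |
|---|---|---|---|---|
| 0.67 | 1.5% | 0.7% | 0.4% | 0.3% |
| 1 | 4.8% | 4.9% | 5.0% | 5.0% |
| 1.25 | 7.9% | 10.1% | 11.3% | 11.7% |
| 1.5 | 11.0% | 15.6% | 18.1% | 19.1% |
| 2 | 15.9% | 25.2% | 30.6% | 32.7% |

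**Check with skewed data.** Lognormal stays, equal means of 6 h, 30 v 1,200, control coefficient of variation (CV) 0.5. The pooled test rejects in 0.3%, 5.1%, 17.8% and 29% of simulations at r = 0.67, 1, 1.5 and 2. Skew with equal spread does not inflate the error.

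**One ANOVA on three groups** (30 / 1,200 / 5,000). With CVs of 1.0 / 0.7 / 0.7 the error is 13.5%; with 1.0 / 0.5 / 0.5 it is 26.5%; with all equal it is 5.8%. The pattern is the same.

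**Overlap.** SI patients are about 1,200 / 60,000 = 2% of the all-ED group. If k participants are among m controls, the control mean is (k × participant mean + (m − k) × mean of the others) / m. The observed difference is then the true one times (1 − k/m). With k = 30 the shrinkage is 2.5% for m = 1,200 and 10% for m = 300. It would be 30% for m = 100, the extreme case in which all 30 enrolled within a one-month extract.

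**Alternatives, same equal-mean setting (30 v 1,200).** Welch on raw hours rejects in 5% to 9% across r = 0.67 to 2 at control CV 0.5. With stronger skew and the same CV in both groups it rejects in 8.4% (CV 1.0) and 11.1% (CV 1.2). Welch on log hours rejects in 15%, 14% and 32% at r = 0.67, 1.5 and 2. It compares geometric means, which differ when the arithmetic means are equal and the spreads are not.

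**Power for a 1.5-fold longer stay** (9 h v 6 h, CV 1.0 in both groups): pooled ANOVA 66%, Welch on raw hours 42%, log-scale t-test 74%. At CV 1.5, ANOVA has 41% and the log-scale test 52%.

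**The case against.** The strongest case against the point has four parts.

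- **The inflation is conditional.** It needs participants to be more variable than controls, and the documents say nothing on that. This stands: every error rate above depends on an assumed SD ratio.
- **The control size is inferred.** The period is undefined, and the SI group, the more relevant one, might number only a few hundred. This stands and lowers the figures, but at 100 controls the error is still 11% to 16% for ratios of 1.5 to 2.
- **The ANOVA sentence follows text on comparing the randomised groups and does not name length of stay.** That is so, but it is the only rule for continuous variables. For the randomised comparison of 15 v 15 the method does little harm: simulated error is 4.0% with equal CVs and 7.4% with CVs of 1.0 v 0.5.
- **The consequence is small.** Length of stay appears under Other measures, is not one of Outcomes 1 to 4, and feeds no decision rule in this pilot. This stands and sets the severity.

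A reader might also infer that ANOVA here both inflates error and loses power. Inflation and near-zero rejection belong to opposite scenarios. Nor is a large loss of power for longer stays supported: with equal spread, ANOVA gives 66% against 74% on the log scale at CV 1.0, and more than raw-scale Welch.

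**Conclusion.** The point holds in a limited form. The comparison is planned, the only stated method pools variance across very unequal groups, and as written the groups overlap. The overlap is a matter of text. The error rate depends on assumed SD ratios and control sizes: 18% to 30% at ratios of 1.5 to 2 with 1,200 controls, 11% to 16% with 100, near 5% with equal spread, and 0.4% (1,200 controls) to 1.5% (100 controls) at a ratio of 0.67.

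Two stronger readings are not supported. A reader might infer that this result decides whether the programme is feasible in a busy ED, but the documents attach no feasibility threshold or decision to length of stay. A reader might also infer that moving to a log scale is a free cure. It changes the quantity compared, and if equal mean hours is the question, it rejects too often when spreads differ.

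Severity: consider.

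**What to change.** Add a short paragraph on length of stay to Data Analysis:

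- State the calendar period of both control extracts.
- Exclude participants' visits from both extracts, and SI patients from group (a).
- Compare participants with each control group separately, giving the difference in mean hours with a 95% interval from an unequal-variance method (Welch or bootstrap).
- Report medians and IQRs for all groups alongside.
- Use a log-scale Welch analysis, with a ratio of geometric means, only if that different estimand is declared in advance.

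The cost is analysis wording and two filters on the record extracts; patients do nothing more. There is a statistical price. With a skewed group of 30, Welch on raw hours still has an error rate of about 6% to 9% (11% at CV 1.2). It also has less power than pooled ANOVA for longer stays (42% v 66% at CV 1.0 and a 1.5-fold difference). Reporting length of stay descriptively, without a test, would also be reasonable in a pilot of this size.
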